Dopamine agonists such as pramipexole are efficacious and first-line FDA-approved treatments in low doses for primary (i.e., idiopathic) RLS ([name] et al., 2006, 2016). Dopamine agonists are also efficacious for secondary RLS associated with end-stage renal disease (Pellecchia et al., 2004), peripheral neuropathy (Bastia et al., 2015) and pregnancy (Dostal et al., 2013). A few published case reports suggest that dopamine agonists are also effective in opioid withdrawal-related RLS (Ghosh & Basu, 2014; Park et al., 2010, 2014), and it is not uncommon for opioid detoxification units to have dopamine agonists (e.g., ropinirole, pramipexole) on formulary to address RLS. FDA-approved dopamine agonists not only dramatically reduce core RLS symptoms of leg restlessness and dysesthesia but by this mechanism produce substantial improvements in sleep disturbance in both primary and secondary RLS ([name] et al., 2016). As opioid withdrawal is prominently characterized by sleeplessness (Oyefeso et al., 1997), which is thought to independently confer risk for relapse to opioid use (Beswick et al., 2003), treatment of protracted opioid withdrawal related RLS may also improve sleep in this cohort.

We hypothesize that effective treatment of RLS symptoms with pramipexole is an effective treatment for RLS symptoms in OUD patients during post-detox clinical stabilization. Further, we

hypothesize that treatment of RLS in this context will also improve overall symptoms of opioid withdrawal as assessed by the SOWS. As exploratory aims, we also hypothesize that treatment of RLS symptoms will (i) improve subjective sleep quality and duration and reduce self-reported sleep disruption, and (ii) contribute to longer stays in the inpatient OUD step-down stabilization treatment facility. Retention in treatment – longer stays in the facility with its multi-dimensional treatment strategy options - is highly correlated with success in OUD outcomes. (Fleury et al., 2016).

II. SPECIFIC AIMS

Primary Aim:

• To determine whether pramipexole will have significantly greater effect than placebo in reducing RLS symptoms in OUD patients immediately following acute opioid withdrawal during post-detox clinical stabilization

Secondary Aim:

• To determine whether pramipexole will have significantly greater effect than placebo in reducing self-reported opioid withdrawal symptoms in OUD patients immediately following acute opioid withdrawal during post-detox clinical stabilization.

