Exploratory Aims:

- To determine whether pramipexole will have significantly greater effect than placebo for self-reported sleep metrics (e.g., quality, disturbance, sleep latency and duration) in OUD patients immediately following acute opioid withdrawal during post-detox clinical stabilization.
- To determine whether OUD patients on pramipexole will stay in the post-detox clinical stabilization unit longer than those on placebo. This will enable a higher rate of successful referral to after-care than those on placebo.

III. SUBJECT SELECTION

The following lists the inclusion/exclusion criteria for prospective participants.

Inclusion Criteria:

- 1. Men or women of any ethnic origin.
- 2. Written informed consent is obtained
- 3. Speaks and writes in English
- 4. A willingness and ability to comply with study procedures.
- 5. Age 18–75 years

- 6. Patients with diagnosed OUD who have undergone primary detoxification for their OUD in any detox facility, have been transferred to the Gavin Clinical Stabilization Service (CSS), and have some persistent opioid withdrawal as indicated by a SOWS>1 on Day 1
- 7. Diagnosis of RLS from the Hening Telephone Diagnostic Interview (HTDI) with subsequent confirmation by clinical interview conducted by a study physician (e.g., [name], [name])
- 8. International Restless Legs Syndrome Severity Scale (IRLS) Symptoms subscale score of >11 for three consecutive days prior to randomization. Participants who miss one day of questionnaires prior to randomization may be included if the IRLS subscale score is >11 for each day questionnaires are completed.

Exclusion Criteria:

- 1. Pregnant. Gavin Foundation staff perform pregnancy tests upon admission to the CSS.
- 2. Participants with active or unstable major psychiatric disorder other than OUD, who, in the investigators' judgement, require further treatment
- 3. Neurological disorder or cardiovascular disease raising safety concerns about use of pramipexole and/or judged to interfere with ability to assess efficacy of the treatment
- 4. Medical instability considered to interfere with study procedures
- 5. Stage 3, 4, or 5 renal insufficiency
- 6. Participation in this study on a previous admission to the CSS

IV. SUBJECT RECRUITMENT AND ENROLLMENT

Methods of recruitment and procedures for informed consent:

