Screening Run-In (3 days): The participant will receive daily email links to an online sleep diary and three questionnaires: the IRLS subscale, SOWS, and an opioid craving visual analog scale. Baseline subjective sleep measures will be determined from this 3-day period.

RANDOMIZATION VISIT (VISIT 3) AND TREATMENT PERIOD:

A more thorough medical history will be collected at the Randomization Visit, along with demographic information. At this visit, the 3-day sleep diary and questionnaire results will be reviewed for final eligibility before the participant is randomized to treatment.

Eligible participants will be randomized in a 1:1 ratio to 10 days of placebo or pramipexole. Pramipexole will be started at 0.25 mg nightly for the first 3 days. On day 3, a study physician will call the participant over the phone or on video to inquire about efficacy and adverse events (Visit 4). Visit 4 may occur on day 4 or 5 if the study physician is unable to meet on day 3. If the 0.25-mg dose is well tolerated but not effective, the dose can be increased to 0.5 mg.

Participants will receive medication from the Gavin Foundation staff and will complete the online sleep diary and questionnaires every day (see the Table of Procedures below for the exact schedule). Gavin Foundation staff will direct participants to the secure computer on which they can complete the sleep diary and questionnaires.

FINAL STUDY VISIT (VISIT 5):

On Day 10, participants will meet with a study physician. The physician will assess the participant on the Clinical Global Impression-Improvement (CGI-I) scale and will also inquire about any adverse events experienced. If a participant is discharged from the Gavin Foundation CSS before Day 10, study staff will attempt to perform Visit 5 before his or her departure from the facility.

Compensation:

Participants will be remunerated. Any earnings will be loaded onto a debit card, which will be given to the participant when he or she leaves the Gavin Foundation CSS.

Participants will be paid based on completion of sleep diaries and questionnaires after receiving study drug.

The payment schedule is as follows:

- \$5/day for filling out diaries and questionnaires on the 10 days on study drug
- \$25 for fully completing the study (i.e. spending 10 days on the study drug and completing 10 days of diary entries)

The total possible compensation is \$75.

[figure not shown]

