The key secondary variables are the difference from randomization to Day 5 and from randomization to Day 10 in SOWS.

Exploratory analyses will similarly focus on the differences from randomization to Day 5 and from randomization to Day 10. These endpoints include:

- 1. Subjective total sleep time
- 2. Subjective sleep latency
- 3. Subjective time awake after sleep onset
- 4. Depressive (PHQ-9) and anxiety (GAD-7) symptoms
- 5. Time spent in the Gavin CSS

STATISTICAL METHODS

Interim analysis:

(i) Two-sample t-tests will be applied to estimate the effect of randomized treatment group on IRLS subscale score, for the subjects with post-randomization data to date. Using the estimated treatment effect, we will conduct a power analysis to determine the sample size necessary to detect this effect. (i) Two-sample t-tests will be applied to estimate the effect of randomized treatment group on SOWS, for the subjects with post-randomization data to date. Using the estimated treatment effect, we will conduct a power analysis to determine the sample size necessary to detect this effect.

Primary analysis:

(i) Two-sample t-tests will be applied to compare the change in IRLS subscale from randomization to Day 5 and from randomization to Day 10 between the two groups. (ii) Linear mixed-effects models will also be applied to the longitudinally measured IRLS subscale with entry of covariates that correlate with changes in primary endpoints as required (e.g., age, sex, and at-randomization levels of IRLS severity, and SOWS). Subjective sleep measures from the sleep diary for every night of data collection will also be added as potential covariates to the linear mixed-effects models.

Secondary Analysis:

(i) Two-sample t-tests will be applied to compare the change in SOWS from baseline to Day 5 and to Day 10 between the two groups. (ii) Linear mixed-effects models will also be applied to longitudinally measured SOWS with entry of covariates that correlate with changes in primary endpoints as required (e.g., age, sex, and at-randomization levels of IRLS severity, and SOWS).

Subjective sleep measures on every night of data collection will also be added as potential covariates to the linear mixed-effects models.

Exploratory Analyses:

Linear and generalized linear mixed-effects models will be applied to compare changes in the self-reported sleep metrics (e.g., quality, disturbance, sleep latency and duration) across the nights of study and between the groups.

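### The mixed model may adjust for outcome-selected covariates and on-treatment sleep, and the Day 10 t-test has no rule for a missing Day 10 value

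*Combined protocol and SAP*

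**What the plan says.** **Tests.** Section IX, Statistical Methods, Primary analysis, begins: "Two-sample t-tests will be applied to compare the change in IRLS subscale from randomization to Day 5 and from randomization to Day 10". Item (ii) of the same paragraph adds linear mixed-effects models on the longitudinal IRLS subscale. The Secondary Analysis repeats this structure for SOWS. Under Power/Sample Size, Aim 1, the trial is sized on the Day 10 t-test with 34 per group.

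**Covariates.** The mixed models are fitted "with entry of covariates that correlate with changes in primary endpoints as required". Age, sex and at-randomization IRLS and SOWS are given only as examples. Then: "Subjective sleep measures from the sleep diary for every night of data collection will also be added as potential covariates". The Table of Procedures has the diary on every day through Day 10, so this includes nights on treatment. The run-in supplies a separate baseline: "Baseline subjective sleep measures will be determined from this 3-day period".

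**Expected effects.** Section I hypothesises that treatment will "improve subjective sleep quality and duration and reduce self-reported sleep disruption" and "contribute to longer stays in the inpatient OUD step-down stabilization treatment facility". It attributes the sleep benefit of dopamine agonists to relief of core RLS symptoms. An exploratory aim is: "To determine whether OUD patients on pramipexole will stay in the post-detox clinical stabilization unit longer than those on placebo".

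**Patients analysed.** The intent-to-treat (ITT) set needs one dose and one post-randomization assessment. The per-protocol set needs 10 days of evaluable data. The plan randomizes 88 to have 68 complete. For early discharge, "study staff will attempt to perform Visit 5 before his or her departure from the facility". No section says how a missing Day 10 value is handled, or whether an early Visit 5 counts as Day 10.

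**The concern.** **Covariates.** On-treatment sleep is a consequence of treatment and, by the plan's own reasoning, of the IRLS improvement itself. A treatment effect adjusted for it no longer answers the primary question, because the part shared with sleep is taken out. Choosing covariates by their correlation with the outcome also leaves the model open to choice after the data are seen. The two rules reinforce each other: a measure expected to follow RLS symptoms is one that a correlation rule would tend to select.

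**Missing Day 10 values.** A Day 10 change cannot be computed without a Day 10 value. The ITT and per-protocol Day 10 t-tests would therefore rest on much the same 68 or so patients, although the ITT set is defined more widely. The plan itself hypothesises that length of stay differs by arm, so unequal exit is a foreseeable outcome. The mixed model uses every available value and is the natural protection, so a loose covariate rule weakens the analysis best placed to help.

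**Working it through.** **1. The plan's own figures (Power/Sample Size, Aim 1).** Difference 6.3, SD of change 9.0, 34 per group, two-sided alpha 0.05.
- Standardized effect = 6.3/9.0 = 0.70. Noncentrality = 0.70 x sqrt(34/2) = 2.89 on 66 df. Power = 81.2%, against 80% stated, so it reproduces.
- Completers = 2 x 34 = 68. Non-completers = 88 - 68 = 20, and 20/88 = 22.7%.

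Effects below are best read as shares of the planned effect. The sizing text speaks of the IRLS scale, while the endpoint is a five-item subscale.

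**2. Adjusting for on-treatment sleep.** Let q be the within-arm correlation of IRLS change with sleep improvement, and s the drug effect on sleep in SD units. The documents give neither, so both are assumptions. For one adjusted comparison at Day 10 (65 df):
- adjusted effect = 0.70 - q x s
- residual SD = sqrt(1 - q^2)
- variance of the treatment coefficient multiplied by 1 + s^2/4, because sleep differs between arms

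(a) Sleep improves only through RLS relief, as Section I describes. Then s = 0.70 x q and the proportional cut is q^2.

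| q | s | Adjusted effect | Cut | Power |
|---|---|---|---|---|
| 0.3 | 0.21 | 0.637 | 9% | 77.0% |
| 0.5 | 0.35 | 0.525 | 25% | 67.9% |

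(b) The drug also has its own effect on sleep, so s exceeds 0.70 x q.

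| q | s | Adjusted effect | Cut | Power |
|---|---|---|---|---|
| 0.3 | 0.3 | 0.61 | 12.9% | 72.9% |
| 0.3 | 0.5 | 0.55 | 21.4% | 62.2% |
| 0.5 | 0.5 | 0.45 | 35.7% | 53.5% |

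The decimals are for tracing the arithmetic only. This is a one-visit approximation to the longitudinal model.

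(c) No true IRLS effect. Under (a), s = 0 and adjustment shifts nothing. If the drug acts on sleep alone, the estimate shifts by -q x s. For q and s from 0.3 to 0.5 that is 0.09 to 0.25 SD against pramipexole.

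**3. Missing Day 10 values.** Suppose patients who leave improve g points less than those who stay, by the same g in both arms. Then bias in the completer difference = (exit rate on drug - exit rate on placebo) x g. With 20 exits from 44 + 44 and g assumed at 3 to 9:
- 10 v 10: 0.
- 8 v 12 (drug v placebo): (0.182 - 0.273) x g = -0.27 to -0.82.
- 6 v 14: (0.136 - 0.318) x g = -0.55 to -1.64.

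The range of -0.27 to -1.64 is 4 to 26% of 6.3, against pramipexole. The sign reverses if the better responders leave, or if the drug arm loses more. If leaving is unrelated to response, g = 0 and there is no bias.

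**4. At the reported size.** The note at the end of Section IX reports 35 randomized. At the planned completion rate, 35 x 68/88 = 27 would have Day 10 data. A simulation assumed baseline SD at 0.5 to 1 times the Day 10 SD and between-visit correlation of 0.3 to 0.5 (500 trials per setting, standard error about 2 points). Power was 42-43% for the t-test, 36-47% for an unstructured mixed model and 45-55% for a random-intercept model. The random intercept was the true structure in these runs, which favours it.

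**The case against.** - **Sleep measures are only potential covariates, and the named examples are all baseline variables.** True, so the harm is conditional. But the only stated criterion for entry is correlation with the outcome, which on-treatment sleep is likely to meet.
- **The t-test comes first and carries no covariates.** True. A reader might infer that the headline result is distorted by sleep adjustment. The documents do not support that, because the problem is confined to the mixed model.
- **Dropout is already budgeted.** True. A reader might infer that the trial ignores dropout or is underpowered for it. It is not: 68 completers give 81% for IRLS. The Day 5 t-test should lose fewer patients, the mixed model uses all values, and staff try to see early leavers. What is unwritten is only how a missing Day 10 value is handled.
- **Bias is not shown.** True. A reader might infer that the Day 10 t-test is biased, perhaps in favour of pramipexole. The plan hypothesises a difference in length of stay but does not link leaving to response. If placebo loses more of its poorer responders, the bias runs against the drug.
- **A mixed model need not gain power, and this is a pilot that may stop near 35 randomized.** This stands against insisting on one elaborate model. It does not excuse loose covariate rules, because the plan states formal power at alpha 0.05.
- **An early-discharge IRLS may not exist.** Fair. The Visit 5 text names only the clinical global impression and adverse events, although the Table of Procedures places an IRLS at V5.

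**Conclusion.** The covariate rule is the firmer half. Followed as written, it can put on-treatment sleep into the IRLS and SOWS models and absorb part of the treatment effect. For IRLS the cut is 9 to 25% under the plan's own account of how sleep improves, and up to about 36% if the drug also acts on sleep separately. Both figures rest on assumed correlations of 0.3 to 0.5, and the second also on an assumed sleep effect of up to 0.5 SD.

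The missing Day 10 half is real but smaller. About 20 of 88 ITT patients may have no value for the test that sizes the trial, and no rule covers them. Whether this biases the result depends on who leaves, which the documents do not settle. The all-values mixed model already guards against exit that depends on observed scores, and only partly against exit that depends on unobserved ones.

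The plan should be changed on both points. The case does not rest on power.

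**What to change.** 1. **Covariates, IRLS and SOWS.** Replace the selection rule with a fixed list of pre-randomization measures, for example age, sex, at-randomization IRLS and SOWS, and the run-in sleep baseline. Delete selection by correlation with the outcome. Delete the nightly post-randomization sleep measures, or label sleep-adjusted models exploratory.
2. **Day 10 comparison.** Take the ITT comparison as the Day 10 treatment difference from that mixed model, using all post-randomization values of the ITT set, with the t-test as a supportive completer analysis. If the t-test stays primary, state how a missing Day 10 value is handled and do not count an early-discharge Visit 5 as Day 10.
3. **Sensitivity.** Add one missing-not-at-random analysis, for example a delta adjustment varied by arm.

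Covariance structure, fallback and visit windows are optional details.

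**Cost.** Analysis-plan wording and a little programming, with no new data. Settle it before those who write it see any result by arm, including the interim one. The model relies on missing-at-random. At about 35 randomized an unstructured covariance may have less power than the t-test, so a simpler structure may be needed.

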Linear and generalized linear mixed-effects models and survival-based analyses will be applied to compare the number of days patients continue in CSS treatment between the two groups.

Power/Sample Size:

Power calculations are based on Specific Aims 1 and 2 detailed below. There are insufficient published or unpublished data to perform them on exploratory analyses (detailed above). Meta-analyses of RLS clinical trials indicate that placebo effects using the IRLS are strongly related to the duration of these trials (Fulda et al., 2008). Therefore, we are basing our calculations on short-term trials, similar to our study design, for pramipexole in RLS using abbreviated RLS symptom scales (e.g., Oertel et al., 2007; Manconi et al., 2007, 2012)

Aim 1: The primary outcome is the change in IRLS scale from baseline to Day 10. Using the Oertel et al. (2007) data as reference, with n=34 for each group, we will have 80% power to detect a 6.3 points difference in the change of IRLS scale (with a common standard deviation of the change of 9.0) with a two-sided two-sample t-test at alpha=0.05 level. A change of 3 is considered a clinically meaningful difference from placebo (Allen et al., 2013).

Aim 2: The primary outcome is the change in SOWS. Using the Dunn et al. (2017) data as reference, with n=34, we will have 80% power to detect a 4 points difference in the change of SOWS (with a common standard deviation of the change of 6.0) with a two-sided two-sample t-test at alpha=0.05 level.

Therefore, our plan is to enroll 160 people in a 1:1 drug:placebo ratio in order to randomize 88 patients with OUD and have 68 participants complete the 10-day trial. With approximately 16 patients per week admitted to the CSS with opioid use disorder, and an RLS prevalence of 50% in this context, we do not anticipate any difficulty enrolling to our target sample size for the trial within a 20-month enrollment period.

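### The named t-tests on change make no use of baseline, and the mixed models adjust for it only conditionally; a fixed, prespecified baseline adjustment should decide each outcome

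*Combined protocol and SAP*

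**What the plan says.** Under Statistical Methods, Primary analysis, two items are listed. Item (i) reads "Two-sample t-tests will be applied to compare the change in IRLS subscale from randomization to Day 5" and continues to Day 10. Item (ii) reads "Linear mixed-effects models will also be applied to the longitudinally measured IRLS subscale", followed by "with entry of covariates that correlate with changes in primary endpoints as required (e.g., age, sex, and at-randomization levels of IRLS severity, and SOWS". The same paragraph also makes the nightly sleep-diary measures potential covariates in the mixed models.

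The Secondary Analysis has the same structure: "Two-sample t-tests will be applied to compare the change in SOWS from baseline to Day 5 and to Day 10", then "Linear mixed-effects models will also be applied to longitudinally measured SOWS", with the same covariate wording and the same provision for sleep measures.

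Power/Sample Size refers only to the two-sample t-test: "with n=34 for each group, we will have 80% power to detect a 6.3 points difference in the change of IRLS scale". The SD assumed for that change is 9.0. The SOWS calculation has the same form, with a 4-point difference and an SD of 6.0.

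Baseline values are available. The run-in collects "three questionnaires: the IRLS subscale, SOWS, and an opioid craving visual analog scale", and the Table of Procedures marks IRLS and SOWS on Days -2, -1 and 0.

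**The concern.** A t-test on change amounts to fixing the regression slope of follow-up on baseline at 1. If the true slope differs from 1, baseline still predicts change, and that predictable part stays in the error variance. Patients enter on repeated IRLS subscale scores above 11, so some regression to the mean is expected and an IRLS slope of exactly 1 is unlikely.

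Item (ii) could recover this precision but does not guarantee it. Baseline appears only as an example of a covariate, and it enters according to a correlation seen in the data. Nothing says whether item (i) or item (ii) decides the result. The mixed model may also include sleep measured after randomization. The Background hypothesizes that treatment improves sleep, so conditioning on those nights could absorb part of the treatment effect.

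What is at stake is precision in a small trial that recruits slowly (35 randomized in two years), and freedom to choose between analyses after the data are seen.

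**Working it through.** **Inputs from Power/Sample Size.** 34 per arm (the SOWS text gives n=34, taken as per arm); two-sided alpha 0.05; IRLS difference 6.3, SD of change 9.0; SOWS difference 4, SD of change 6.0.

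**Step 1: the plan's own figures.** SE = SD × sqrt(2/34), with noncentral t on 66 df.
- IRLS: SE = 9.0 × sqrt(2/34) = 2.183; 6.3/2.183 = 2.886; power 81.2%. The stated 80% is reproduced.
- SOWS: SE = 6.0 × sqrt(2/34) = 1.455; 4/1.455 = 2.749; power 77.3%. The stated 80% is slightly optimistic.

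**Step 2: variance left after adjustment.** Let rho be the correlation of baseline with follow-up. With equal variances at the two times, ANCOVA residual variance divided by the variance of change is (1 + rho)/2: 0.65, 0.75 and 0.85 at rho 0.3, 0.5 and 0.7. The documents give no rho, so this range is assumed.

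**Step 3: charge the cost.** One covariate leaves 65 df and inflates the variance by 1 + 1/64 on average for chance imbalance. Adjusted SE = SD × sqrt(ratio) × sqrt((2/34) × 65/64). Example, IRLS at rho 0.5: 9.0 × sqrt(0.75) = 7.79; SE = 1.905; 6.3/1.905 = 3.307; power 90.3%.

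| rho | Ratio | IRLS power | SOWS power | IRLS n per arm for 80% |
|---|---|---|---|---|
| t-test | 1 | 81.2% | 77.3% | 34 |
| 0.3 | 0.65 | 93.8% | 91.5% | 23 |
| 0.5 | 0.75 | 90.3% | 87.3% | 26 |
| 0.7 | 0.85 | 86.4% | 83.0% | 29 |

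The IRLS difference detectable with 80% power falls from 6.21 to between 5.04 and 5.77 points.

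**Step 4: allow for the IRLS entry rule.** Selecting on baseline narrows its spread but leaves the slope b unchanged. Assume equal unrestricted variances and a baseline SD cut to 0.6 of its unrestricted value. The ratio is then (1 + b)/(1 + b + 0.36 × (1 − b)), with the SD of change among those enrolled held at 9.0.
- b = 0.3: 1.3/1.552 = 0.838; IRLS power 86.9%.
- b = 0.5: 1.5/1.680 = 0.893; IRLS power 84.8%.
- b = 0.7: 1.7/1.808 = 0.940; IRLS power 82.9%.

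**Step 5: worst case.** If baseline is unrelated to change, the ratio is 1 and only the cost remains: IRLS 81.2% to 80.5%, SOWS 77.3% to 76.6%. This can occur within plausible inputs. With baseline SD 0.6 of follow-up SD and rho 0.6, the general ratio (1 − rho²)/(k² + 1 − 2 × rho × k), where k is that SD ratio, is 0.64/0.64 = 1.

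**Step 6: simulation check.** With 20,000 trials per setting and 34 per arm, ANCOVA power for IRLS was 93.7%, 90.2% and 86.2% without restriction at rho 0.3, 0.5 and 0.7. With baseline cut at its population mean it was 87.5%, 84.9% and 82.9%. Type I error was 4.6% to 5.3% for both methods across the settings run.

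**The case against.** The strongest reply is that the plan already provides for baseline adjustment. Item (ii) sits under the same heading as the t-test and names IRLS and SOWS at randomization. A reader who looks only at item (i) might infer that no adjustment is planned, and the documents do not support that. What is missing is narrower: a baseline term that is always in the model, and a statement that this model decides.

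A second reply is that the t-test on change is valid, prespecified and consistent with the sample-size basis. That stands. One might infer that chance baseline imbalance biases it, but under 1:1 randomization it is unbiased on average, and its standard error already reflects such imbalance. Adjustment buys precision only.

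A third is that the gain is unknown and may be small. This also stands. The equal-variance figures are the optimistic end for IRLS because of the entry rule, and the restricted case gives about 2 to 6 points. The regression-to-the-mean argument from entry is made for IRLS; SOWS needs only a score above 1 on Day 1. Nor is adjustment strictly free, as the worst case shows.

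**Conclusion.** The concern holds as a recommendation on efficiency and prespecification, not as an error that invalidates the analysis. Under the assumed correlations, a fixed baseline term adds about 5 to 13 points of IRLS power and 6 to 14 points of SOWS power with equal variances. For IRLS the gain is about 2 to 6 points if entry narrows the baseline spread as assumed. Against this stands a loss of at most about 0.7 points if baseline does not predict change.

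The absolute powers also rest on the plan's SDs. The 9.0 is stated for the IRLS scale, whereas the endpoint is a five-item subscale with 24-hour recall. The variance ratios do not depend on that SD. The case for settling which analysis decides, and with which covariates, does not depend on any assumed correlation.

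**What to change.** For each outcome, name one deciding analysis: an ANCOVA of the Day 10 score on arm, or the Day 10 treatment contrast from the mixed model. Include that outcome's own Day 0 value as a covariate in every case. List any further baseline covariates in advance rather than selecting them by observed correlation. Keep sleep measures recorded after randomization out of the model that estimates the treatment effect. Retain the change-score t-test as a sensitivity analysis.

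For consistency, use the adjusted estimate and residual variance in the interim sample-size calculation too. It also relies on t-tests, and its result decides whether the study continues.

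The cost is a few sentences in the analysis sections, settled before anyone involved in the choice sees unblinded results, plus one degree of freedom per outcome for its Day 0 term. No new data are needed.
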